- Withdrawal of Approval: If an IRB withdraws the approval to conduct this study for any reason, the investigator will notify the Sponsor as soon as possible, but in no event later than five working days after the withdrawal of the approval
- Progress Reports: The investigator will submit progress reports on the investigation to the Sponsor and the reviewing IRB at regular intervals, but in no event less often than yearly.
- Deviations from the Investigational Plan: The investigator must notify the Sponsor and the reviewing IRB of any deviation from the Investigational Plan to protect the life or physical well-being of a subject in an emergency. This notice must occur as soon as possible, but in no case longer than five working days following the occurrence of the deviation.
- Informed Consent: If the investigator uses a device without obtaining informed consent, the investigator shall report the use to the Sponsor and the IRB within 5 working days after the use occurs.
- Final Report: Within three months after the termination or completion of the study or the investigator's part in the study, the investigator shall submit a final report to the Sponsor and the IRB.
- Other Reports: Upon request from the IRB or the FDA, the investigator shall provide accurate, complete and current information about any aspect of the study.

Each investigator is responsible for ensuring that the study is conducted according to this protocol and that signed Informed Consent is obtained from each subject prior to their inclusion in this study.

11. Adverse Events and Serious Adverse Events

General

All observed or volunteered adverse events regardless of treatment group or suspected causal relationship to the investigational product(s) will be reported as described in the following sections.

For all adverse events, the investigator must pursue and obtain information adequate both to determine the outcome of the adverse event and to assess whether it meets the criteria for classification as a serious adverse event requiring immediate notification to the Hologenix contact. For all adverse events, sufficient information should be obtained by the investigator to determine the causality of the adverse event. The investigator is required to assess causality. For adverse events with a causal relationship to the device, follow-up by the investigator is

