required until the event or its sequelae resolve or stabilize at a level acceptable to the investigator, and the Hologenix contact concurs with that assessment.

Adverse Event Reporting

For serious adverse events, the reporting period to Hologenix or its designated representative begins from the time that the subject provides informed consent, which is obtained prior to the subject's participation in the study, i.e., prior to undergoing any study-related procedure and/or receiving investigational product, through and including 28 calendar days after the last administration of the investigational product. Any serious adverse event occurring any time after the reporting period must be promptly reported if a causal relationship to investigational product is suspected. Adverse events (serious and non-serious) should be recorded on the CRF from the time the subject has undergone one treatment through last subject visit.

Definition of an Adverse Event (AE)

An adverse event is any untoward medical occurrence in a clinical investigation subject administered a product or medical device; the event need not necessarily have a causal relationship with the treatment or usage. Examples of adverse events include but are not limited to:

- Abnormal test findings;
- Clinically significant symptoms and signs or diagnosis;
- Changes in physical examination findings;
- Hypersensitivity;
- Progression/worsening of wound.

Protocol Specific AE Definition/Collection

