For the purposes of this study, only AEs that are directly related to the study product, diabetes (including labs & kidney function) or wound healing (including infections related to the wound) will be collected and reported as these events may affect outcomes and analysis of data. AEs not related to the aforementioned product or diagnoses are not relevant to the subject outcomes of this research or data analysis (such as nausea, emesis, pain, constipation, diarrhea, mood disorders, respiratory diagnoses, cardiac related events, etc). AEs that do not fall under this protocol specific definition will be assessed and treated as per standard of care. SAEs will be collected as per the usual SAE guidelines (see section on reporting SAEs). In addition, planned procedures related to the study wound for a subject during the same hospitalization (as these subjects will be recruited while in the hospital because they have an infection in their foot wound/ulcer) for incision/debridement/amputation will be considered part of their continuation of SOC and not adverse events unless a complication, new infection or new wound occurs.

Definition of Serious Adverse Event (SAE)

A Serious Adverse Event (SAE) is any AE that has any serious unfavorable and unintended sign, symptom, or disease temporally associated with the use of the devices, whether or not considered related, including those that:

- · results in death
- is life-threatening
- requires inpatient hospitalization or causes prolongation of existing hospitalization
- results in persistent or significant disability/incapacity
- is a congenital anomaly/birth defect
- requires intervention to prevent permanent impairment or damage

Medical and scientific judgment should be exercised in determining whether an event is an important medical event. An important medical event may not be immediately life-threatening and/or result in death or hospitalization. However, the important medical event should be reported as serious, if it is determined that the event may jeopardize the subject and/or may require intervention to prevent one of the other adverse event outcomes.

Causality Assessment of Adverse Events

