The investigator's assessment of causality must be provided for all adverse events (serious and non-serious); the investigator must record the causal relationship in the CRF, as appropriate, and report such an assessment in accordance with the serious adverse reporting requirements if applicable. An investigator's causality assessment is the determination of whether there exists a reasonable possibility that the cleared medical device caused or contributed to an adverse event. If the investigator does not know whether or not medical device caused the event, then the event will be handled as "related to medical device" for reporting purposes. (see Section on Reporting Requirements). If the investigator's causality assessment is "unknown but not related to investigational product", this should be clearly documented on study records.

In addition, if the investigator determines a serious adverse event is associated with study procedures, the investigator must record this causal relationship in the source documents and CRF, as appropriate, and report such an assessment in accordance with the serious adverse event reporting requirements, if applicable.

Adverse Event Severity Assessment

The Investigator will provide an assessment of the severity of each adverse reaction by recording a severity rating on the appropriate SAE reporting page of the subject's file. Severity, which is a description of the intensity of manifestation of the SAE, is distinct from seriousness, which implies a patient outcome or SAE-required treatment measure associated with a threat to life or functionality. Severity will be assessed according to the following scale.

If required on the adverse event case report forms, the investigator will use the adjectives MILD, MODERATE, or SEVERE to describe the maximum intensity of the adverse event. For purposes of consistency, these intensity grades are defined as follows:

MILD	Does not interfere with subject's usual function.
MODERATE	Interferes to some extent with subject's usual function.
SEVERE	Interferes significantly with subject's usual function.

Note the distinction between the severity and the seriousness of an adverse event. A severe event is not necessarily a serious event. For example, a headache may be severe (interferes significantly with subject's usual function) but would not be classified as serious unless it met one of the criteria for serious adverse events, listed above.

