Withdrawal Due to Adverse Events (See Also Section on Subject Withdrawal)

Withdrawal due to adverse event should be distinguished from withdrawal due to insufficient response, according to the definition of adverse event noted earlier, and recorded on the appropriate adverse event CRF page.

When a subject withdraws due to a serious adverse event, the serious adverse event must be reported in accordance with the reporting requirements defined below.

Eliciting Adverse Event Information

The investigator is to report all directly observed adverse events and all adverse events spontaneously reported by the study subject. In addition, each study subject will be questioned about adverse events by a member of the research staff.

Reporting Requirements

Each adverse event is to be assessed to determine if it meets the criteria for serious adverse events. If a serious adverse event occurs, expedited reporting will follow local and international regulations, as appropriate.

Serious Adverse Event Reporting Requirements

If a serious adverse event occurs, Hologenix is to be notified within 24 hours of awareness of the event by the investigator. In particular, if the serious adverse event is fatal or life-threatening, notification to Hologenix must be made immediately, irrespective of the extent of available adverse event information. This timeframe also applies to additional new information (follow-up) on previously forwarded serious adverse event reports as well as to the initial and follow-up reporting of Exposure during pregnancy cases.

In the rare event that the investigator or member of the research team does not become aware of the occurrence of a serious adverse event immediately (e.g., if an outpatient study subject

initially seeks treatment elsewhere), the investigator or member of the research team is to report the event within 24 hours after learning of it and document the time of his/her first awareness of the adverse event.

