For all serious adverse events, the investigator is obligated to pursue and provide information to Hologenix in accordance with the timeframes for reporting specified above. In addition, an investigator may be requested by Hologenix to obtain specific additional follow-up information in an expedited fashion. This information may be more detailed than that captured on the adverse event case report form. In general, this will include a description of the adverse event in sufficient detail to allow for a complete medical assessment of the case and independent determination of possible causality. Information on other possible causes of the event, such as concomitant medications and illnesses must be provided. In the case of a subject death, a summary of available autopsy findings and/or a copy of the death certificate must be submitted as soon as possible to Hologenix or its designated representative.

All AEs/SAEs should be followed until resolution.

Non-Serious Adverse Event Reporting Requirements

All adverse events will be reported on the adverse event page(s) of the CRF. It should be noted that the form for collection of serious adverse event information is not the same as the adverse event CRF. Where the same data are collected, the forms must be completed in a consistent manner. For example, the same adverse event term should be used on both forms. Adverse events should be reported using concise medical terminology on the CRFs as well as on the form for collection of serious adverse event information.

Reporting Requirements to Regulatory Authorities

Adverse events reporting, including suspected serious unexpected adverse reactions, will be carried out in accordance with applicable local regulations.

12. Committees

Data and Safety Monitoring Board

The study will be under the oversight of an independent DSMB that will assess the accumulated safety data on an ongoing basis. The role and responsibilities of the DSMB will be predefined in the DSMB charter.

13. Publication Policy

The preparation and submittal for publication of manuscripts containing the study results shall be in accordance with a process determined by mutual written agreement among the investigator and the Hologenix contact. The publication or presentation of any study results shall comply with all applicable privacy laws, including, but not limited to, the Health Insurance Portability and Accountability Act of 1996.

PI: [name]

14. Bibliography

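### Non-serious adverse events are collected only if judged related to the sock, diabetes or wound healing, yet later sections require all of them and the safety tables are labelled as if all were there

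*Combined protocol and SAP*

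**What the plan says.** Section 11 contains two collection rules for non-serious adverse events.

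**Narrow rule.** Protocol Specific AE Definition/Collection says that "only AEs that are directly related to the study product, diabetes (including labs & kidney function) or wound healing" will be collected and reported. It adds that "AEs not related to the aforementioned product or diagnoses are not relevant to the subject outcomes of this research or data analysis", and its examples of such events include pain, without saying where. SAEs are exempt and follow the usual rules.

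**Wide rule.** Definition of an Adverse Event says that "the event need not necessarily have a causal relationship with the treatment or usage". Adverse Event Reporting says: "Adverse events (serious and non-serious) should be recorded on the CRF from the time the subject has undergone one treatment through last subject visit". After the narrow rule come Eliciting Adverse Event Information ("The investigator is to report all directly observed adverse events and all adverse events spontaneously reported by the study subject") and Non-Serious Adverse Event Reporting Requirements ("All adverse events will be reported on the adverse event page(s) of the CRF"). Neither refers back to the narrow rule or carries a qualifier.

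**Analysis.** Section 4, Safety Endpoints and Analyses, tabulates all AEs, SAEs and procedure-related AEs by treatment. A separate table covers device-specific risks, including mild pain or discomfort. The risk table under Benefits and Risks, Potential Risk, gives four items for that category: ache around the dressing area, perspiration from the sock, decreased sleep, and paresthesia.

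**The concern.** A coordinator cannot obey both rules, and the safety counts depend on which one is followed. Under the narrow rule, the all-AEs table cannot hold what its label says. The plan itself separates related events from all events, because study-related AEs and SAEs appear as their own item in the list of secondary endpoints in Section 4.

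The device-risk row matters more. In a blinded randomised trial, listed risks can be compared between arms without anyone deciding what caused each event. Filtering on judged cause before the data reach the CRF gives up part of that advantage. Section 2 requires subjects to be willing to wear the sock at least 22 hours a day, so disturbed sleep is a plausible device effect. It is also one that an investigator could attribute to something else.

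**Working it through.** The plan states no figure to reproduce. The conflict is one of text, and the only arithmetic is illustrative.

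**1. Does the order of the sections resolve the conflict?** Section 11, General, says "All observed or volunteered adverse events regardless of treatment group or suspected causal relationship to the investigational product(s) will be reported", but as described in the sections that follow, so it can yield to the narrow rule. The eliciting and non-serious reporting sections cannot be read that way. They are themselves following sections, they come after the narrow rule, and they say all without a limit.

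**2. What passes the filter?** Causality Assessment says: "If the investigator does not know whether or not medical device caused the event, then the event will be handled as" related to the device. Only events positively judged unrelated are therefore dropped.

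| Item in the pain/discomfort category | Link to product, diabetes or wound | Exposure to the filter |
|---|---|---|
| Ache around the dressing area | Local to the wound | Mostly passes |
| Perspiration | Tied to the sock by its wording | Mostly passes |
| Paresthesia | Readily attributed to diabetes | Some may be lost |
| Decreased sleep | None built in | Most exposed |

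The ranking is an inference from the wording; the documents do not state it. Some aches could also be lost, because pain is a named exclusion.

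**3. Can the effect on the arm comparison be sized?** Not from the documents, which give no AE rates. As an illustration, assume 127 per arm, a 10% background rate (b) in both arms, and a 10-point sock-caused excess (e). Let rb and re be the shares of background and excess that the filter keeps.

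- Control expected count = 127 × b × rb
- Celliant expected count = 127 × (b × rb + e × re)
- Flag = probability that a pooled two-proportion z test at one-sided 0.025 is significant, by exact binomial enumeration. Section 4 plans no such test; it serves only as a yardstick.
- Subjects lost = (12.7 + 25.4) minus the two filtered counts

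| rb / re | Control | Celliant | Flag | Subjects lost |
|---|---|---|---|---|
| 100% / 100% | 12.7 | 25.4 | 0.610 | 0 |
| 75% / 75% | 9.5 | 19.1 | 0.477 | 9.5 |
| 50% / 50% | 6.4 | 12.7 | 0.325 | 19.1 |
| 50% / 75% | 6.4 | 15.9 | 0.574 | 15.9 |
| 75% / 90% | 9.5 | 21.0 | 0.605 | 7.6 |
| 50% / 90% | 6.4 | 17.8 | 0.707 | 14.0 |

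The filter lowers both counts in every case. The flag probability falls in four cases and rises in one, so the direction depends on shares that nobody knows. The last column also gives the extra subjects with an AE page if the filter is lifted for this category: about 8 to 19 of 254.

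**The case against.** The strongest defence is that the specific rule governs the general one. The narrow rule is headed as protocol-specific and is stated to apply for this study. The Executive Summary defines the safety endpoint as the incidence of events reported. On that view, all AEs in Section 4 means all events collected under the protocol definition, and sleep loss judged unrelated by a blinded investigator is not a device-specific risk. This is a fair reading of the intent. It does not remove the conflict with the two later sections, and the table label would still need the qualifier.

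Two stronger inferences are tempting and do not hold.

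- *The omitted events are gone for good.* Section 9, Source Documents, makes the occurrence and status of any adverse event part of the minimum medical record, with no relatedness filter. Section 3, Trial Monitoring, gives monitors access to the records. The filter acts between source and CRF, so such events may be retrievable.
- *The filter hides harm from the sock or favours one arm.* The same blinded judgement applies in both arms, and the illustration shows that detection can move either way.

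Other channels also capture discomfort: VAS pain at the treatment visits, early termination for a 50% rise in pain, questions on sock wear and changes, and listed withdrawals. They do little for sleep. The DFS-SF sleep item asks about difficulty because of foot ulcers and is scheduled only at the end-of-study visit. The documents do not say that the DSMB would see events left off the CRF.

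**Conclusion.** The concern holds as a minor point. The inconsistency is plain in the text and rests on no assumption. Under the narrow rule, the all-AEs table leaves out non-serious events judged unrelated, and the mild pain or discomfort row is filtered on causality. The loss is confined to events positively judged unrelated. That decreased sleep is the main casualty is a reasonable inference, not a documented fact.

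SAEs and the primary and key secondary analyses are untouched. Section 4 plans safety counts only, with no test or confidence interval. The illustrative rates are assumptions throughout and support no claim about how many events would be missed or which arm would look better.

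**What to change.** **Section 11, Protocol Specific AE Definition/Collection.** From first sock application, record on the CRF every non-serious AE that falls in a category of the Potential Risk table or affects the study foot, whatever its judged cause. Make causality a separate field. Limit the excluded example of pain to pain elsewhere than the study foot. Other unrelated non-serious events may stay uncollected.

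**Section 11, General, Adverse Event Reporting, Definition, Eliciting, and Non-Serious Reporting.** Refer to this one rule.

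**Section 4, Safety Endpoints and Analyses.** Label the first table as all collected AEs, and state that the device-risk table counts events irrespective of causality.

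**Subjects enrolled before the change.** Retrieve such events from the medical records where they are documented. Flag or split the device-risk table only where retrieval is incomplete.

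**Cost.** One paragraph, some cross-references and two phrases. Staff already question subjects about adverse events. The downside is more minor AE pages and more background noise: about 8 to 19 more subjects of 254 on the illustrative rates, plus any added by the study-foot trigger, and the work of record retrieval.

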- Presence of osteomyelitis that requires treatment outside the study scope.
- Need for wound management outside the study scope

Celliant Clinical Trial Protocol
PI: [name]
Protocol #: HGX2020-01

 Or for any reason that may, in the opinion of the Investigator, affect negatively the wellbeing of the subject.

If for any reason the subject is withdrawn from the clinical investigation, the Investigator will inform the subject accordingly.

3. Clinical Investigation Plan

Description of Trial Design

This study is designed as a prospective, multi-center, double-blind, 1:1 randomized clinical trial to assess the clinical safety and efficacy of Celliant® Diabetic Medical Socks to increase tissue oxygenation and complete wound closure.

Investigational Sites

University of Texas Southwestern, Department of Plastic Surgery

PI: [name], DPM, MPH

Location: Dallas, TX

Parkland Hospital, Department of Plastic Surgery

PI: [name], DPM Location: Dallas, TX

Duration of Subject Participation

- Screening: Within 7 days Run-In initiation
- Run in Evaluation: 2 weeks of evaluation
- Treatment period: Up to 12 weeks
- Follow-up period: Up to 3 months post wound closure event
- Total duration of subject participation: Up to 28 weeks

Screening and Enrollment

Patients who present to the investigator's institution (through clinic admission, direct transfer from another facility, or through the emergency room) may be recruited to participate in the study. No direct marketing for subject recruitment will be done.

Patients approached for study participation will be at least 22 years of age at the time of consent, will undergo wound assessment, and meet all eligibility requirements. Those meeting eligibility criteria for the study will have the study explained to them by the Investigator. An Informed Consent Form will be provided to sign according to Section 11 prior to undergoing any study procedures. Patients will be encouraged to ask questions of the investigators. It will be made clear to the patient that not participating in the study will in no way influence the treatment plan or the relationship with the physician.

Celliant Clinical Trial Protocol
Protocol #: HGX2020-01

Wound Selection

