- 8. Perform SPP and tcPO2 measurements at Visit 4 (maybe be taken instead at visit 5 or 6 if subject has not been wearing their treatment sock leading up to the visit or misses this visit).
- 9. Collect all relevant concomitant medication
- 10. Perform pain assessment.
- 11. Redress the wound with standard of care (if wound is still active) and apply Celliant Active or Control Sock and apply offloading (if indicated).
- 12. Wound will be offloaded.
- 13. Provide subject with any additional medical socks needed until the next visit. Instruct the subject to change the socks if they become wet, soiled, or bloody and under any conditions dictated by PI instructions. Instruct the subject that they must wear the sock at all times and that including the 3 hours leading up to the next study visit.

Study Visit - Wound Closed

- 1. The study wound is defined as closed when there is complete skin re-epithelialization without drainage or dressing requirements confirmed by the evaluating physician at 2 consecutive study visits 2 weeks apart.
- 2. At this visit the subject will perform the EOS evaluation and enter the follow-up phase of the study.

Study Visit 12/EOS

- 1. If the study wound closes prior to the 12-week study mark, subjects will perform EOS visit at the time of wound closure. See Study Visit Wound Closed.
- 2. A subject whose wound does not close completely by week 12 will exited from the study after the week 12 wound evaluation.
- 3. Document study compliance information from the subject
 - a. Amount of time the sock was worn throughout the week
 - b. Was it worn during the day/night?
 - c. When/why the sock was changed.

- d. Has the sock been on in the 3 hours leading up to the appointment?
- 4. Remove sock and dressing and immediately perform hyperspectral imaging of the dorsal and plantar aspects of the foot if wound is active or closed.
- 5. Assess target ulcer (if wound has closed, document as such, perform steps 7-12 and skip to Study Visit Wound Closed).
- 6. If the subject still has a large enough wound, collect 4 tissue samples. Two in RNA later and two in DNA/RNA shield.
- 7. Perform standardized photography of the study wound.
- 8. Assess the ulcer area (cm²), perimeter (cm), and greatest depth (cm) using the inSight device.
- 9. Perform SPP if wound is active or closed.
- 10. Perform tcpO2 if wound is active or closed.
- 11. Perform pain assessment
- 12. Ask the subject if they thought they were in the active or control group

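### The plan has no rule for scoring an amputated or surgically removed study ulcer for complete closure, and its adverse event exemption for planned amputation is not tied to consent

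*Combined protocol and SAP*

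**What the plan says.** **Adverse event exemption.** Section 11 (Protocol Specific AE Definition/Collection) exempts "planned procedures related to the study wound for a subject during the same hospitalization". It explains that subjects are recruited in hospital with an infected foot ulcer, and provides that "incision/debridement/amputation will be considered part of their continuation of SOC and not adverse events unless a complication, new infection or new wound occurs". Nothing says when the procedure must have been planned.

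**Serious events.** The next heading states: "A Serious Adverse Event (SAE) is any AE that has any serious unfavorable and unintended sign, symptom, or disease". Serious events are otherwise to be collected under the usual guidelines, with reporting from consent onward. For the case report form, "Adverse events (serious and non-serious) should be recorded on the CRF from the time the subject has undergone one treatment through last subject visit".

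**Safety tables.** Section 4 (Safety Endpoints and Analyses) tabulates adverse events, serious adverse events, procedure-related adverse events and device-specific risks. It has no amputation row, and amputation is not an endpoint.

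**Closure.** Section 3 (Study Visit - Wound Closed) says: "The study wound is defined as closed when there is complete skin re-epithelialization without drainage or dressing requirements". A physician must confirm this at two consecutive visits two weeks apart. Amputation, excision and surgical closure are not mentioned.

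**Termination and standard of care.** One reason for early termination in Section 2 (Withdrawal of Subjects) is "Need for wound management outside the study scope". Study scope is not defined. The Standard of Care text in Section 3 covers debridement, dressings and offloading, and does not list amputation.

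**Missing closure outcomes.** Section 4 (Handling of Missing Data) calls for five multiply imputed datasets if week-12 closure is missing in more than 7.5% of subjects, and also a non-imputed analysis.

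**The concern.** The background section presents amputation as a leading consequence of diabetic foot ulcers, so a reader will expect it to be counted by arm and not to be able to register as healing. As drafted, neither is assured.

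On safety, a study-wound amputation decided after consent but within the recruiting admission can be called planned. It then has no route into any safety table.

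On efficacy, complete closure is the key secondary endpoint, and its result at 254 evaluable subjects drives early stopping, futility and sample size re-estimation. Loss of the ulcer to surgery is a treatment failure in any ordinary reading, yet the plan leaves its score to site judgment or to an imputation model.

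**Working it through.** **1. Does the exemption reach serious events?** A serious event must first be an adverse event, and an exempt procedure is not one. It is therefore not a serious event either, although hospitalization or disability criteria might otherwise fit. This follows by inference from the definition; no separate exemption for serious events is written.

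**2. Is amputation inside the study scope?**

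| Place | Treatment of amputation |
|---|---|
| Section 11, AE definition | Continuation of standard of care, if planned and in the recruiting admission |
| Section 3, Standard of Care | Not listed |
| Section 2, Withdrawal | Not named; management outside an undefined scope ends participation |

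These cannot all be applied consistently.

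**3. How would an amputated subject be scored for closure?**

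- *Retained:* once the site is covered by skin, dry and free of dressings at two visits, the written definition can be met.
- *Terminated before confirmation:* the week-12 outcome is missing. At 7.5% missing or less, the subject has no value in the logistic model. Above 7.5%, the value is imputed and may be closed. Expected attrition of 5 to 15% spans the threshold, so either branch is possible.
- In neither case does a rule make the subject a failure, even though the primary population is intent-to-treat.

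**4. Scale.** Inputs from Section 4 (Sample Size Justification): 25% vs 20% closure, 2500 evaluable subjects (1250 per arm), two-sided 0.05, power about 0.85.

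Power = Φ[(d − 1.96·se₀)/se₁], with se₀ = √(2p̄(1−p̄)/n) and se₁ = √((p₁(1−p₁)+p₂(1−p₂))/n).

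Plan's own figure: p̄ = 0.225, se₀ = 0.01670, se₁ = 0.01667, so (0.05 − 0.03274)/0.01667 = 1.035 and power = 0.850. It reproduces.

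The documents give no amputation rate, so the rates below are **assumptions**.

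*(a) A share a of each arm is amputated and counted closed.* Then p₁ = 0.25 + 0.75a and p₂ = 0.20 + 0.80a.

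| a | Difference (points) | Power, N = 2500 |
|---|---|---|
| 0 | 5.00 | 0.850 |
| 1% | 4.95 | 0.834 |
| 2% | 4.90 | 0.818 |
| 3% | 4.85 | 0.802 |
| 5% | 4.75 | 0.769 |

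*(b) No true effect (20% vs 20%), with an excess of false closures in the active arm.* Probability of one-sided rejection at 0.025, fixed design:

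| Excess (points) | N = 508 | N = 2500 |
|---|---|---|
| 0 | 0.025 | 0.025 |
| 0.5 | 0.034 | 0.050 |
| 1 | 0.046 | 0.090 |
| 2 | 0.080 | 0.232 |
| 3 | 0.128 | 0.447 |

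*(c) Terminated instead of retained, 2% of each arm.* That is 0.02 × 1250 = 25 subjects per arm. If left out, the rates become 0.25/0.98 = 25.5% and 0.20/0.98 = 20.4%. If imputed as closed with probability 0.20 to 0.25 (assumed), they add 5 to 6.25 false closures per arm, or 0.4 to 0.5 points.

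These figures ignore covariate adjustment and the adaptive design.

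**The case against.** The strongest reply is about timing. The exemption is confined to the recruiting admission. Randomization follows a run-in of about two weeks, to which qualified subjects return as outpatients. A change of 30% or more in ulcer area at either run-in visit is a screen failure, so an ulcer removed after baseline would probably never be randomized. Most exempt procedures would therefore belong to no arm and precede case report form recording of adverse events. An amputation in a later admission is not exempt. Worsening of the wound and wound infection remain reportable, and a surgical wound might itself be read as a new wound, which would void the exemption.

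Much of this stands and limits the exposure. It does not close the gap. Serious event reporting starts at consent, so a pre-randomization amputation that is exempt still leaves that stream. Whether a surgical wound counts as new should not be left to interpretation. And the timing argument concerns the exemption only; closure scoring is undefined for any amputation of the study ulcer.

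A reader might infer that nothing stops an amputated subject from counting as healed, or that such a subject stays in the trial. The documents do not support either. The outside-scope criterion could end participation, and the standard-of-care list favours that reading. It is not a firm barrier, because Section 11 calls the procedure standard of care.

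A reader might also note that six false closures in one arm of 127 are 6/127 = 4.7 points, about the whole planned effect. That assumes every event falls in one arm at the interim. The standard error of the difference there, at 20% closure, is √(2 × 0.20 × 0.80/127) = 5.0 points, so the shift is about 0.9 standard errors. At 1250 per arm, six events are 0.48 points. The exemption applies equally to both arms of a double-blind trial, and the documents suggest no source of imbalance.

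**Conclusion.** The concern holds as a moderate defect with two parts. First, the exemption lacks a consent anchor, so a study-wound amputation decided after consent in the recruiting admission can be absent from every safety table; after randomization this exposure is narrow. Second, and more broadly, no explicit rule scores an amputated or surgically closed study ulcer, and the outcome may be closed, missing or imputed.

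The size is unknown because no event rate is given. On the assumed rates, a balanced 1 to 5% costs roughly 2 to 8 points of power at 2500 subjects, and material type I error inflation requires an excess of false closures in the active arm. The documents do not support a claim that amputations generally vanish from safety reporting or are routinely credited as healing.

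**What to change.** 1. **Section 11:** limit the exemption to procedures already planned and documented before consent. Record every study-limb amputation after randomization and tabulate it by arm, whatever its adverse event status. List those between consent and randomization.
2. **Section 3 closure definition and Section 4 key secondary analysis:** state that a study ulcer removed by amputation or closed surgically counts as not closed at 12 weeks, and is neither treated as missing nor imputed.
3. **Sections 2, 3 and 11:** reconcile the termination criterion, the standard-of-care list and the exemption on whether amputation is within study scope. Which reading applies is for the sponsor and investigators to settle.

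The cost is a few sentences in an amendment, one safety table row and one listing. Reported event counts may rise slightly and closure rates may fall slightly. The sample size need not change if the planned 25% and 20% refer to closure without surgical removal.
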